1. PROTOCOL SUMMARY

1.1 Synopsis

1.1.1 Study overview

This study will evaluate the safety and immunogenicity of two different dosages of a novel peroxide-inactivated whole-virus yellow fever vaccine, HydroVax-002 YFV, in healthy adults. The currently available yellow fever vaccine is the live, attenuated YFV-17D vaccine. This live attenuated vaccine is contraindicated in multiple vulnerable populations including infants <9 months of age and immunosuppressed individuals such as those with acquired immunodeficiency syndrome, thymic disease, or persons with hypersensitivity to eggs. Special precautions are also noted for pregnant women, nursing mothers and adults over the age of 60 [1]. These contraindications and precautions stem from known serious adverse events associated with the vaccine including a serious nervous system/neurotropic condition termed yellow fever associated neurotropic disease (YEL-AND). In addition to YEL-AND, vaccination with live YFV-17D can cause severe multiple organ system failure, described as yellow fever vaccine-associated viscerotropic disease (YEL-AVD), a syndrome closely resembling wild-type yellow fever virus (YFV). Because HydroVax-002 YFV is based on inactivated virus that is unable to replicate or spread to the brain or nervous system, we anticipate that these vaccine complications will be eliminated.

1.1.2 Enrollment Period

It is anticipated that enrollment may be completed in 3.5-4 months.

1.1.3 General

This trial will be a randomized, placebo controlled, double-blind (within dosing group), dose escalation Phase 1 trial evaluating dosages of 1 mcg and 5 mcg of HydroVax-002 YFV vaccine given intramuscularly on Day 1 (the day of first vaccination is defined as Day 1) and Day 29 in healthy adults ≥ 18 and <50 years of age. The study will consist of two dosing groups of HydroVax-002 YFV vaccine to be enrolled sequentially. Each dose group will consist of 10 individuals who receive HydroVax-002 YFV and 2 or 3 who receive placebo. The initial dose of HydroVax-002 YFV to be evaluated in Group 1 will be 1 mcg and the next dose to be evaluated in Group 2 will be 5 mcg. Following assessment of safety and reactogenicity data of Group 1 by the Safety Monitoring Committee (SMC), the vaccine dose will be increased to 5 mcg for Group 2. All participants will be monitored for local and systemic solicited adverse events for 7 days following each vaccination, unsolicited adverse events for 28 days following each vaccination, and for the occurrence of new onset chronic medical conditions and serious adverse events from the time of first vaccination until 6 months following the second vaccination. Safety laboratory tests will be performed prior to vaccination and at days 4 and 15 following vaccination. YFV neutralizing assays will be performed on blood samples collected prior to each vaccine, 15 days following each vaccine, and at days 29, 57, and 180 following the second dose of vaccine.

For each dosing group, the first four subjects enrolled (the sentinel subgroup) will include three HydroVax-002 YFV recipients and one placebo recipient. After the four subjects in the Group 1 sentinel subgroup are enrolled and given their first vaccination, enrollment will then be stopped pending a review of the clinical laboratory, reactogenicity, and safety data collected through the post vaccination Day 8 visit for the last of those subjects.

This review may be conducted by an internal safety review committee (ISRC), consisting of the Blinded medical monitor, clinical program manager, and the PI, or by the SMC, as indicated and detailed in Section [10.1.6](#). Approval by the reviewing group will allow administration of the second vaccination to the sentinel subgroup and continued enrollment of the remaining 9 Group 1 subjects (expanded group) to resume to complete enrollment of 13 participants (10 vaccine and 3 placebo).

After Group 1 enrollment is completed enrollment will be stopped pending an SMC review of the clinical laboratory, reactogenicity, and adverse event information through the post 2nd vaccination Day 15 visit for all Group 1 subjects. Approval by the SMC will allow escalation to Group 2, and initiation of enrollment of the Group 2 sentinel subgroup. After the four subjects in the Group 2 sentinel subgroup are enrolled and given their first vaccination, enrollment will then be stopped pending a safety review of the sentinel subgroup as specified for the low dose cohort. Approval will allow administration of vaccination 2 to the sentinel subgroup and continued enrollment of Group 2 subjects (expanded group) to complete study enrollment.

This study will accrue 25 participants: (10 receiving 1 mcg of HydroVax-002 YFV; 10 receiving 5 mcg of HydroVax-002 YFV; and 5 receiving placebo).

1.1.4 Study Population

Healthy, male and female adults ≥ 18 and < 50 years of age

1.1.5 Inclusion Criteria

1. Provide written informed consent prior to initiation of any study procedures.
2. Are able to understand and comply with planned study procedures and be available for all study visits.
3. Must agree to the collection of venous blood per protocol.
4. Are males or non-pregnant females, ≥ 18 and < 50 years of age, inclusive at time of enrollment.
5. Are in good health¹.

¹As determined by medical history and physical examination to evaluate acute or currently ongoing chronic medical or psychiatric diagnoses or conditions, defined as those that have been present for at least 90 days, which would affect the assessment of the safety of subjects or the immunogenicity of study vaccinations. Chronic medical diagnoses or conditions should be stable for the last 60 days (no hospitalizations, emergency room or urgent care for condition, or invasive medical procedure and no adverse symptoms that need medical intervention such as medication change/supplemental oxygen). This includes no change in chronic prescription medication, dose or in the 60 days prior to enrollment. Any prescription change that is due to change of health care provider, insurance company, etc., or that is done for financial reasons, as long as in the same class of medication, will not be considered a deviation of this inclusion criterion. Subjects may be on chronic or as needed (prn) medications if, in the opinion of the site PI or appropriate sub-investigator, they pose no additional risk to subject safety or assessment of reactogenicity and immunogenicity and do not indicate a worsening or treatment of continued symptoms of medical diagnosis or condition. Note: Low dose topical, corticosteroids as outlined in the Subject Exclusion Criteria (see Section [5.2](#)) as well as herbals, vitamins and supplements are permitted.

6. Oral temperature is less than 100.0°F.
7. Pulse is 47 to 100 beats per minute, inclusive.
8. Systolic blood pressure is 85 to 140 mmHg, inclusive.

9. Diastolic blood pressure is 55 to 90 mmHg, inclusive.
10. Screening laboratories (WBC, Hgb, PLTs, Sodium, Potassium, Bicarbonate, Calcium, Cr, non-fasting glucose, ALT, AST, TBIL and urine protein and glucose) are within acceptable parameters².
²Hematology, blood chemistry and liver enzymes must be Grade 1 or less at screening (Refer to [Table 11](#), [Table 12](#), and [Table 13](#), respectively); urine glucose negative and urine protein no greater than trace at screening for subjects to qualify for randomization and vaccination.
11. Negative test for HIV, hepatitis B virus (HBV), and hepatitis C virus (HCV) at screening blood draw
12. Women of childbearing potential³ must use an acceptable contraception method⁴ from at least 30 days before the first study vaccination until 30 days after the second study vaccination
*³Not sterilized via, bilateral oophorectomy, salpingectomy, hysterectomy, or successful Essure[®] placement (permanent, non-surgical, non-hormonal sterilization) with documented radiological confirmation test at least 90 days after the procedure, and still menstruating or <1 year has passed since the last menses if menopausal.
⁴Includes non-male sexual relationships, full abstinence from sexual intercourse with a male partner, monogamous relationship with vasectomized partner who has been vasectomized for 180 days or more and shown to be azoospermic prior to the subject receiving the study vaccination, effective intrauterine devices, NuvaRing[®], tubal ligation, and licensed hormonal methods such as implants, injectables or oral contraceptives (i.e. “the pill”).*
13. Women of childbearing potential must have a negative serum pregnancy test at screening and a negative urine pregnancy test within 24 hours prior to each study vaccination.
14. Sexually active males must agree to use a medically acceptable form of contraception⁵ in order to be in this study and must agree to continue such use until day 30 after the last vaccination.
⁵Medically acceptable contraceptives include: (1) surgical sterilization (such as a vasectomy), or (2) a condom used with a spermicide. Contraceptive measures such as Plan B[™], sold for emergency use after unprotected sex, are not acceptable methods for routine use.

1.1.6 Exclusion Criteria

1. Have an acute illness¹ or acute febrile illness (oral temperature $\geq 38^{\circ}\text{C}$ [100.4°F]), as determined by the site PI or appropriate sub-investigator, within 72 hours prior to study vaccination.
¹An acute illness which is nearly resolved with only minor residual symptoms remaining is allowable if, in the opinion of the site PI or appropriate sub-investigator, the residual symptoms will not interfere with the ability to assess safety parameters as required by the protocol.
2. Have any medical disease or condition that, in the opinion of the site PI or appropriate sub-investigator, is a contraindication to study participation².
²Including acute, subacute, intermittent or chronic medical disease or condition that would place the subject at an unacceptable risk of injury, render the subject unable to meet the requirements of the protocol, or may interfere with the evaluation of responses or the subject’s successful completion of this trial.
3. Have immunosuppression as a result of an underlying illness or treatment, a recent history or current use of immunosuppressive or immunomodulating disease therapy.
4. Use of anticancer chemotherapy or radiation therapy (cytotoxic) within 3 years prior to study vaccination.
5. Have known active or recently active (12 months) neoplastic disease or a history of any hematologic malignancy. Non-melanoma, treated, skin cancers are permitted.
6. Known allergy to components of the study product³.
³Including the following: aluminum hydroxide, sorbitol, potassium chloride, sodium chloride and polysorbate80 (Tween80)

7. Unstable seizure disorder (defined as requiring medication for seizure control or with seizure activity within the past 3 years).
8. Have a history of alcohol or drug abuse within 5 years prior to study vaccination.
9. Have any diagnosis, current or past, of schizophrenia, bipolar disease or other psychiatric diagnosis that may interfere⁴ with subject compliance or safety evaluations.
⁴As determined by the site PI or appropriate sub-investigator.
10. Have been hospitalized for psychiatric illness, history of suicide attempt, or confinement for danger to self or others within 5 years prior to study vaccination.
11. Have a history of asthma, other than mild, well-controlled asthma⁵
⁵Cold or exercise induced asthma controlled with inhaled medications other than inhaled corticosteroids is permissible. Participants should be excluded if they require daily bronchodilator use, or have had an asthma exacerbation requiring oral/parenteral steroid use or have used theophylline or inhaled corticosteroids in the past year.
12. Have a history of diabetes mellitus.
13. Have taken oral or parenteral (including intra-articular) or chronic topical corticosteroids of any dose within 30 days prior to study vaccination⁶.
⁶Corticosteroid nasal sprays for allergic rhinitis are permissible. Persons using a topical corticosteroid for a limited duration for mild uncomplicated dermatitis such as poison ivy or contact dermatitis may be enrolled the day after their therapy is completed.
14. Have taken high-dose inhaled corticosteroids⁷ within 30 days prior to study vaccination.
⁷High-dose defined as per age as using inhaled high-dose per reference chart in the National Heart, Lung and Blood Institute Guidelines for the Diagnosis and Management of Asthma (EPR-3) or other lists published in UPTODATE.
15. Received or plan to receive a licensed, live vaccine within 30 days before or after each study vaccination.
16. Received or plan to receive a licensed, inactivated vaccine or allergy desensitization shot within 14 days before or after each study vaccination.
17. Received an experimental agent⁸ within 30 days prior to the study vaccination or expect to receive another experimental agent⁹ during the trial-reporting period¹⁰.
*⁸Including vaccine, drug, biologic, device, blood product, or medication.
⁹Other than from participation in this trial.
¹⁰Approximately 7 months after the first study vaccination.*
18. Are participating or plan to participate in another clinical trial with an interventional agent¹¹ that will be received during the trial-reporting period¹².
*¹¹Including licensed or unlicensed vaccine, drug, biologic, device, blood product, or medication.
¹²Approximately 7 months after the first study vaccination.*
19. Female subjects who are breastfeeding or plan to breastfeed from the time of the first study vaccination through 30 days after the last study vaccination.
20. Receipt of blood products or immunoglobulin within six months prior to enrollment.
21. Donation of a unit of blood within 60 days prior to enrollment or intends to donate blood during the study period.
22. Body mass index (BMI) ≥ 35 .

23. History of a visit to South America, sub-Saharan Africa or Southeast Asia lasting one month or more.
 24. Planned travel to areas known to be endemic with Yellow Fever virus during the study period.
 25. History of military service.
 26. History of vaccination against dengue, yellow fever, tick-borne encephalitis, or Japanese encephalitis.
 27. History of vaccination with other flavivirus candidate vaccines.
 28. Attended primary (grade) school in Austria, Germany, Japan, South Korea, India, Thailand, Nepal, Vietnam, or Taiwan (locations where the tick-borne encephalitis vaccine is given).
 29. History of yellow fever.
 30. Plan to have a major change in exercise routine or perform strenuous exercise from 72 hours before any dose of study vaccine/placebo and for 72 hours before any safety laboratories¹³.
- ¹³*Safety laboratories are obtained on Days 4 and 15 following each dose of study product.*
31. Contraindication to intramuscular vaccination of either upper arm (for example, due to lymphadenectomy or obscuring tattoos).

1.1.7 Study Intervention

Investigational Vaccine: HydroVax-002 YFV Yellow Fever Virus (YFV), inactivated vaccine, alum-adsorbed, administered intramuscularly in a two-dose series on Day 1 and Day 29 at a dose of 1 mcg and at a dose of 5 mcg. Controls will receive sterile 0.9% NaCl placebo intramuscularly at days 1 and 29.

1.1.8 Staged Enrollment

For each dosing group, the first four subjects enrolled (the sentinel subgroup) will include three HydroVax-002 YFV recipients and one placebo recipient ([Table 1](#)). After the four subjects in the Group 1 sentinel subgroup are enrolled and given their first vaccination, enrollment will then be stopped pending a review of the clinical laboratory, reactogenicity, and safety data collected through the post vaccination Day 8 visit for the last of those subjects. This review may be conducted by an internal safety review committee (ISRC), consisting of the Blinded medical monitor, clinical program manager, and the PI, or by the SMC, as indicated and detailed in [Section 10.1.6](#). Approval by the reviewing group will allow administration of the second vaccination to the sentinel subgroup and continued enrollment of the remaining 9 Group 1 subjects (expanded group) to resume to complete enrollment of 13 participants (10 vaccine and 3 placebo).

After Group 1 enrollment is completed enrollment will be stopped pending an SMC review of the clinical laboratory, reactogenicity, and adverse event information through the post 2nd vaccination Day 8 visit for all Group 1 subjects. Approval by the SMC will allow escalation to Group 2, and initiation of enrollment of the Group 2 sentinel subgroup. After the four subjects in the Group 2 sentinel subgroup are enrolled and given their first vaccination, enrollment will then be stopped pending a safety review of the sentinel subgroup as specified for the low dose cohort. Approval will allow administration of vaccination 2 to the sentinel subgroup and continued enrollment of Group 2 subjects (expanded group) to complete study enrollment.

Table 1. Study design and dose escalation

Group	Subgroup	HydroVax-002 YFV Dose	No. Subjects	
			HydroVax-002 YFV ¹	Placebo ²
1. Low Dose	Sentinel ³	1 mcg	3	1
	Expanded ⁴	1 mcg	7	2
2. High Dose	Sentinel ³	5 mcg	3	1
	Expanded	5 mcg	7	1
Total			20	5

¹HydroVax-002 YFV will be given as an intramuscular injection at Day 1 and at Day 29

²Placebo will be given as an intramuscular injection at Day 1 and at Day 29

³ISRC review of the clinical laboratory, reactogenicity and adverse event data available from enrollment through the post 1st vaccination Day 8 visit for the first 4 sentinel subjects (3 HydroVax-002 YFV and 1 placebo) will be conducted prior to administration of the second vaccination to the sentinel group and prior to initiation of enrollment of the remaining subjects in the Group. If deemed necessary by the ISRC, the SMC will review the safety data.

⁴SMC review of the clinical laboratory, reactogenicity and adverse event data available from enrollment through the post 2nd vaccination Day15 visit for Group 1 (low dose) (n=13) will be conducted prior to initiation of enrollment in Group 2 (high dose).

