3. STUDY OBJECTIVES AND OUTCOME MEASURES

The overall objective of the study is to evaluate the safety and immunogenicity of two different dose levels of HydroVax-002 YFV.

OBJECTIVES	ENDPOINTS (Outcome Measures)
Primary	

To assess the safety, reactogenicity, and tolerability of the HydroVax-002 YFV vaccine administered intramuscularly in a two-dose series on Days 1 and 29 at a dose of 1 mcg or a dose of 5 mcg
	
 • Occurrence of all serious adverse events (SAEs) at any time during the study • Occurrence of all Grade 3 unsolicited adverse events (AEs) from first vaccination through Day 29 after the second vaccination • Occurrence of all Grade 3 laboratory toxicities from first vaccination through Day 15 after the second vaccination • Occurrence of solicited local AE and reactogenicity signs and symptoms in the 7 days after each vaccination • Occurrence of solicited systemic AE and reactogenicity signs and symptoms in the 7 days after each vaccination • Occurrence of any AE through Day 29 after the second vaccination
Secondary	

To assess YFV-specific neutralizing antibody responses after a first dose and after a second dose of HydroVax-002 YFV vaccine given at dose levels of 1 mcg and 5 mcg
	
 • Percentage of subjects achieving seroconversion ($\geq 1:10$ in plaque reduction neutralizing titer [PRNT₅₀] titer) at Day 29 after first vaccination and at Day 29 after second vaccination • Geometric mean neutralizing titers at Days 15 and 29 after first vaccination and at Days 15, 29, and 57 following second vaccination • Reverse cumulative distribution curve of neutralizing titers on Days 15 and 29 after first vaccination and at Days 15, 29, and 57 after the second vaccination for each dose group and for all dose groups combined
Exploratory	

To assess long-term YFV-specific neutralizing antibody responses after a second dose of HydroVax-002 YFV vaccine given at dose levels of 1 mcg and 5 mcg
	
• Geometric mean neutralizing titers at Day 180 following second vaccination• Reverse cumulative distribution curve of neutralizing titers on Day 180 after the second vaccination for each dose group and for all dose groups combined
---	--

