6.1.3 Dose Escalation

For this Phase 1 first-in-human trial, a conservative dose escalation design will be used, in which each dose group of 10 vaccine recipients, and a total of 5 placebo recipients, is split into two subgroups. The first subgroup, termed the sentinel subgroup, includes 3 vaccine and 1 placebo recipient. In each of the two (1 mcg and 5 mcg) dose phases, enrollment is halted after vaccination of the sentinel subgroup. This allows the opportunity to identify potential early vaccine related adverse events in this subgroup prior to exposure of additional subjects, a design which decreases the risk of multiple serious vaccine related adverse events compared to sequential vaccination of the entire dose group without halting [34]. After enrollment of the expanded subgroups, escalation to the next dose group will be delayed until 14 days of safety data following the second vaccination (corresponding to study Day 15) is available from all subjects in the preceding dose group.

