8.2.2 Safety Clinical Laboratory Tests

Safety labs will be conducted on blood samples obtained on Days 4 and 15 after each vaccination and on the day of, but prior to, administration of the first and second vaccination (day 29 after first vaccination). Safety labs include hematology tests (hemoglobin, WBC, and platelet count) and blood chemistry tests (sodium, potassium, bicarbonate, calcium, creatinine, glucose [non-fasting], ALT, AST, and total bilirubin).

Urine will be tested by dipstick to evaluate glucose, protein, blood, and leukocyte esterase on days 1, 15 and 29 after first vaccination and day 15 after second vaccination.

Safety labs will be tested locally by Duke University Health System Clinical Laboratories.

For laboratory values outside the site's reference ranges, the site PI will document clinical significance in the eCRF. Any result that is deemed clinically significant but does not meet the protocol's grading criteria ([Appendix A](#)) should either be repeated by the study site, or the subject referred for appropriate clinical follow-up.

For any result that meets the protocol's grading criteria (whether or not it is deemed clinically significant), the PI will also assess relationship to study product, action taken with product, and whether the subject was discontinued due to the event. Graded laboratory abnormalities should be followed until either a return to normal or are judged to be stable, as determined by the PI.

In the absence of a diagnosis, any clinical safety laboratory test result that meets the definition of an SAE as determined by the investigator (e.g., life-threatening) must be reported as an SAE using the AE/SAE form set.

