9.4.4 Timing of Analyses

9.4.4.1 Interim Safety Analyses

The blinded medical monitor, clinical program manager, unblinded medical monitor and PI of the clinical laboratory will review data through the Day 15 visit after vaccination 1 for the 4 subjects in the sentinel groups. After the completion of Group 1 enrollment, the SMC will then review the data on all Group 1 subjects through the post 2nd vaccination Day 15 visit. These reviews, however, may not involve any hypothesis testing and will not be considered in estimating the precision of any estimates made at the conclusion of the study.

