10.1.6 Safety Oversight

10.1.6.1 Safety Monitoring Committee (SMC)

The study oversight will be conducted by a SMC which is an independent group of experts that will be established by NTI to monitor subject safety and advise NTI. SMC members will be separate and independent of study personnel participating in this study and should not have scientific, financial or other conflicts of interest related to the study. The SMC will consist of members with appropriate expertise to contribute to the interpretation of the data from this trial.

The primary responsibilities of the SMC are to:

- Review and evaluate the accumulated study safety data in a blinded fashion for participant safety after the low dose cohort prior to proceeding to the high dose cohort, study conduct and progress, and
- Make recommendations to the sponsors concerning the continuation, modification, or termination of the trial.

The operating rules of the SMC will be established in conjunction with NTI guidelines.

The SMC will review the safety laboratory results, reactogenicity data, and adverse event information collected through day 15 following Dose 2 for the Low Dose Cohort. SMC approval is required prior to initiation of enrollment in the High Dose Cohort.

The SMC may also be asked to review safety information on the low dose or high dose sentinel groups as documented in Section [10.1.6.2](#).

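### Protocol 1.1.8 gates escalation to 5 mcg on Group 1 data through Day 8 after dose 2; nine other statements, one of them in the same section, require Day 15

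*Protocol*

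**What the plan says.** The second paragraph of protocol 1.1.8 (Staged Enrollment) stops enrollment once Group 1 is full. The SMC then reviews laboratory data, reactogenicity and "adverse event information through the post 2nd vaccination Day 8 visit for all Group 1 subjects", and its approval opens Group 2 at 5 mcg.

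The other statements of the Group 1 review cut-off are:

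- Table 1 footnote 4, also in 1.1.8: review through the "post 2nd vaccination Day15 visit for Group 1 (low dose) (n=13) will be conducted prior to initiation of enrollment in Group 2".
- Protocol 1.1.3: "adverse event information through the post 2nd vaccination Day 15 visit for all Group 1 subjects". Protocol 4.1 and SAP 4.1 use the same words.
- Protocol 6.1.3: "escalation to the next dose group will be delayed until 14 days of safety data following the second vaccination", which it equates with Day 15. Protocol 4.2 and SAP 4.2 repeat this.
- Protocol 9.4.4.1: "the SMC will then review the data on all Group 1 subjects through the post 2nd vaccination Day 15 visit".
- Protocol 10.1.6.1, the SMC's own section: data "collected through day 15 following Dose 2 for the Low Dose Cohort", with SMC approval needed before the high-dose cohort opens.

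Two other provisions bear on what the cut-off captures. Section 8.2.2 says "Safety labs will be conducted on blood samples obtained on Days 4 and 15 after each vaccination". A primary endpoint in section 3 is "Occurrence of all Grade 3 laboratory toxicities from first vaccination through Day 15 after the second vaccination".

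**The concern.** The sentence sets the minimum data the SMC must see before the first people receive 5 mcg. Sections 4.2 and 6.1.3 call the escalation design conservative and rest that on two weeks of follow-up after dose 2. Section 1.1.8 asks for one week.

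The lost week contains the informative visit. In the Schedule of Assessments, Day 8 after dose 2 (visit 05a) is a phone contact with no vital signs, site evaluation or laboratory draw. Day 15 (visit 06) is in person, with blood safety tests, vital signs, site evaluation and the only scheduled urine dipstick after dose 2. Under 1.1.8 the high-dose group could open before any of these had been done in some or all Group 1 subjects.

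The documents contain no rule on which section prevails when two disagree. A Day 8 review would therefore comply with 1.1.8 and breach 10.1.6.1.

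**Working it through.** **1. Reproduce the plan's own figure.** Vaccination day is Day 1, so days of follow-up = study day − 1. Day 15 gives 15 − 1 = 14 days, matching the 14 days in 4.2, 6.1.3 and SAP 4.2. Day 8 gives 8 − 1 = 7 days, half of that.

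**2. Count the statements.**

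| Cut-off after dose 2 | Where | Count |
|---|---|---|
| Day 8 | Protocol 1.1.8 body text | 1 |
| Day 15 | Protocol 1.1.3, Table 1 footnote 4, 4.1, 4.2, 6.1.3, 9.4.4.1, 10.1.6.1 | 7 |
| Day 15 | SAP 4.1, 4.2 | 2 |

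That is nine to one. Section 9.4.4.1 describes the SMC review without saying that escalation waits for it; leaving it out makes the count eight to one. The escalation sentence in 1.1.8 matches the one in 1.1.3 except for the day number, and the amendment history (10.4) records no change to this cut-off.

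**3. Gap between the cut-offs.** Nominally 15 − 8 = 7 days. The visit windows are +1 for Day 8 and ±1 for Day 15, so the shortest gap is 14 − 9 = 5 days and the longest is 16 − 8 = 8 days.

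**4. Safety tests held at each cut-off.** Inputs are the Schedule of Assessments and 8.2.2. The assumptions are that all 13 Group 1 subjects receive both doses and attend every visit, and that each subject's data are cut at that subject's own visit.

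| Tests | Per subject | Through Day 15 | Through Day 8 |
|---|---|---|---|
| Blood, after dose 2 (Days 4, 15) | 2 | 2 × 13 = 26 | 1 × 13 = 13 (50%) |
| Urine, after dose 2 (Day 15) | 1 | 1 × 13 = 13 | 0 |
| Blood, all after dose 1 (Days 4, 15, 29; then 4, 15) | 5 | 5 × 13 = 65 | 4 × 13 = 52 (80%) |
| Urine, all after dose 1 (Days 15, 29; then 15) | 3 | 3 × 13 = 39 | 2 × 13 = 26 (67%) |

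**5. Illustration of what would go unseen.** Suppose a urine abnormality first appears after dose 2 and is present at the Day 15 dipstick. The chance of at least one case among 10 vaccinees is 1 − (1 − p)^10:

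- p = 5%: 1 − 0.95^10 = 40.1%
- p = 10%: 1 − 0.90^10 = 65.1%
- p = 15%: 1 − 0.85^10 = 80.3%

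These agree with protocol Table 8 and apply at a Day 15 cut-off. At Day 8 no scheduled test could show such a case.

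**The case against.** The strongest reply is that nobody would be misled. The wrong sentence is in the synopsis, while 4.1, 6.1.3 and 10.1.6.1 all say Day 15. Following Day 8 would mean ignoring a footnote in the same section and the SMC's own rule. This stands as a limit on the likelihood of harm. It does not make the sentence right.

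There are also backstops. The halting rules in 7.1.1 run regardless of the review cut-off: one related SAE, or the same related Grade 3 unsolicited or laboratory event in two subjects, stops dosing. Group 2 itself begins with four sentinels and a pause. These would limit exposure after a late signal, but they act after the first subjects have received 5 mcg.

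The 13-of-26 and 0-of-13 counts are the strict reading. If the SMC instead saw everything accrued when the last subject reached Day 8, it would have more. Put the last sentinel's first dose at day 0 and second at day 28. The earliest expanded subject is dosed on days 7 and 35 and reaches Day 8 after dose 2 on day 42. By then the last sentinel is at Day 15 after dose 2 (Day 12 if the full +3 window for dose 2 was used). On nominal timing the four sentinels' Day 15 samples would add up to 4, giving 13 + 4 = 17 of 26 blood panels and 4 of 13 dipsticks. Staggered enrollment could add more. Data through a given visit is still most naturally read as a cut at each subject's own visit, and on either reading the last subject lacks Day 15 data.

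The urine illustration is hypothetical: the documents name no such risk, and unscheduled tests are allowed if indicated. The plan also accepts Day 8 after dose 1 for the sentinel review. That review releases more subjects at the same dose, and second doses to the sentinels; it does not raise the dose.

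Finally, SAP section 2 says in the past tense that the dose was increased, so escalation may already have happened. Then the question becomes which data the SMC used.

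**Conclusion.** The concern holds. The 1.1.8 sentence is wrong as written, and the intended cut-off of Day 15 after dose 2 is not in doubt. The error halves the required follow-up before escalation and, on a per-subject cut with full attendance, removes half of the scheduled post-dose-2 blood panels and all of the post-dose-2 dipsticks. It would also let escalation precede the close of the Grade 3 laboratory endpoint window in Group 1. Harm depends on someone acting on 1.1.8 instead of 10.1.6.1. The correction should nonetheless be mandatory, because this is a decision threshold for a first-in-human dose increase and the protocol should give one answer.

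**What to change.** In the escalation sentence of protocol 1.1.8, change Day 8 to Day 15. All ten statements then agree. If Group 2 has already opened, confirm on file that the SMC review used Group 1 data through Day 15 after dose 2.

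Three smaller corrections to the sentinel review can go in the same amendment; none of them drives the conclusion above.

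- **Protocol 9.4.4.1** puts the sentinel review at Day 15 after dose 1 and adds an unblinded medical monitor. Sections 1.1.3, 1.1.8, 4.1 and 10.1.6.2, Table 1 footnote 3 and SAP 4.1 say Day 8. Align it to Day 8 and to the internal safety review committee named in 10.1.6.2: blinded medical monitor, clinical program manager and PI.
- **SAP 4.1** still lists a medical officer on that committee. Remove the role.
- **Protocol 10.1.6.2** leaves unclear whether two different Grade 3 events in two sentinel subjects pass. State which. This matters only for events that meet no individual halting rule, since 7.1.2 already covers a Grade 3 event without alternative etiology within 7 days of dose 1.

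The cost is one number, one sentence, one title and one clause, with no added visits, tests or staff.
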